**Novo Nordisk**

(E) and the event rate per 100 years of exposure (R). Separate summaries are made by severity considering all episodes, nocturnal and daytime episodes using Novo Nordisk and ADA classified episodes. All episodes will also be summarised by category, including summaries in relation to time since start of meal, as occurring during 0.5, 1, 2, and 4 hours after start of meal, and from 2 hours (exclusive) to 4 hours (inclusive) after start of meal, respectively.

The number of treatment emergent severe or BG confirmed hypoglycaemic episodes (all, daytime, nocturnal, 0.5, 1, 2, and 4 hours and from 2 hours (exclusive) to 4 hours (inclusive) after start of the meal) will be analysed based on the FAS using a negative binomial regression model with a log-link function and the logarithm of the time period in which a hypoglycaemic episode is considered treatment emergent as offset. The model will include treatment and stratification (T1DM/T2DM), as factors. To the extent where data allow, separate analysis will be performed for severe hypoglycaemic episodes.

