## Before initiation of the meal test

The subject should be instructed to:

- Follow normal routine regarding eating and exercise habits on the day prior to the meal test
- Refrain from intake of alcohol and use of medications that affect motility (i.e. prokinetics, anticholinergics, tricyclic antidepressants) on the day prior to the meal test, unless the subject was on this medication at trial entry and does not change the product or product dose
- Remember to bring their current/trial bolus and basal insulins, diary and BG meter to the meal test visits
- Attend the meal test visits in a fasting condition. For definition of fasting, please refer to Section 8.1.5. If subjects are normally dosing basal insulin in the morning, as well as metformin dosing in the morning, it is important they wait until after completion of the meal test
- Achieve an SMPG value within a range of 4.0-8.8 mmol/L [71-160 mg/dL] before beginning the meal test. The SMPG value should be verified at the site before starting the meal test

The meal test should be re-scheduled within the visit window and at V10 before randomisation to trial product in case:

- Any hypoglycaemic episode occurs from midnight before the meal test
- The subject is not fasting or
- The SMPG value is outside the range

At V10 (randomisation visit) the investigator must evaluate if the subject is eligible to continue in the trial before the meal test is performed. Only subjects eligible for randomisation should have the V10 meal test performed. Thus, this assessment should not be performed for run-in failure subjects. Randomisation should not take place before the meal test has ended.

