## Initiation of meal test

The subject's body weight must be measured before start and a blood sample must be drawn two minutes before intake of the standardised meal.

Protocol  
Trial ID: NN1218-4357  
UTN: U1111-1197-8289

~~CONFIDENTIAL~~

Date: 30 November 2020 | **Novo Nordisk**  
Version: 5.0  
Status: Final  
Page: 47 of 105

For the meal test at V10 the subject must receive the bolus insulin (NovoRapid®) that was used in the run-in period.

For the meal test at V26 or V26A (for subjects who have prematurely discontinued trial products) the subject should receive the bolus trial insulin they were randomised to and have used throughout the treatment period.

The start of consumption of the liquid meal is defined as time point 0. The subject must consume the liquid meal as quickly as possible and within 12 minutes. The investigator should confirm that the subject consumed the required volume of the standardised liquid meal in the eCRF.

**Table 8–1** Meal test schedule

Time point (minutes)	Blood sample	SMPG values	Standardised meal	Bolus insulin injection
Before start of meal test		X (within target range 4.0-8.8 mmol/L [71-160 mg/dL])		
-2	X			
0			X	X Insulin injection at the start of the meal
15				
30	X	X (as appropriate to ensure subject's safety)		
60	X			
120	X			
180	X			
End of meal test		X (for subject's safety)		

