#### 8.4.2 Hypoglycaemic episodes

Plasma glucose (PG) should always be measured and recorded when a hypoglycaemic episode is suspected.

All PG values:

- $\leq 3.9$  mmol/L (70 mg/dL) or
- $> 3.9$  mmol/L (70 mg/dL) occurring in conjunction with hypoglycaemic symptoms

should be reported in the diary by the subject from V2 to V27 (FU1) In case a subject is not able to fill in the diary e.g. in case of a fatal event, then investigator will be allowed to report the hypoglycaemic episode in the eCRF.

Upon onset of a hypoglycaemic episode the subject is recommended to measure PG every 15 minutes until the SMPG value is  $>3.9$  mmol/L (70 mg/dL) and/or symptoms have been resolved in accordance to current guidelines.

A SMPG value  $\leq 3.9$  mmol/L (70 mg/dL) or hypoglycaemic symptoms must trigger a hypoglycaemic episode form to be completed by the subject. Repeated SMPG measurements and/or symptoms, occurring within a period of 60 min after onset on a hypoglycaemic episode, will by default be considered as one hypoglycaemic episode until a succeeding SMPG value is  $>3.9$  mmol/L (70 mg/dL) and/or symptoms have been resolved and should be reported on one hypoglycaemic episode form. SMPG measurements  $\leq 3.9$  mmol/L (70 mg/dL) or hypoglycaemic symptoms after the 60 min period shall trigger the reporting of a new hypoglycaemia episode and prompt the subject to fill out a new hypoglycaemic episode form until a succeeding measurement is  $>3.9$  mmol/L (70 mg/dL) and/or symptoms have been resolved.

In case of several low SMPG values within the 60 minutes interval, the lowest value is the one that will be reported as the SMPG value for the hypoglycaemic episode but the start time of the episode will remain as the time for the first SMPG value and/or symptom.

The record should include the following information:

- Start date and time of the hypoglycaemic episode
- The PG level before treating the episode (if available) and any follow up measurements  
The lowest value measured during the hypoglycaemic episode will be reported as the PG value for the episode, the remaining values will be kept as source data in the diary

Protocol  
Trial ID: NN1218-4357  
UTN: U1111-1197-8289

CONFIDENTIAL

Date:  
Version:  
Status:  
Page:

30 November 2020  
5.0  
Final  
53 of 105

Novo Nordisk

- Whether the episode was symptomatic (Yes/No)  

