### Classification of Hypoglycaemia

Treatment emergent: hypoglycaemic episodes will be defined as treatment emergent if the onset of the episode occurs on or after the first day of exposure to randomised treatment, and no later than one day after the last day of exposure to randomised treatment.

Nocturnal hypoglycaemic episodes: episodes occurring between 00:01 and 05.59 both inclusive.

[figure not shown]
Hypoglycaemic episodes are classified according to the Novo Nordisk classification of hypoglycaemia (see [Figure 17-1](#)) and the ADA classification of hypoglycaemia (see [Figure 17-2](#)).

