4.4.1.2 Safety Analysis

In terms of AEs, as a minimum, SAEs will be tabulated.

Number of treatment emergent adverse events

AEs will be coded using the Medical Dictionary for Regulatory Activities (MedDRA). AEs will be presented based on system organ class and preferred terms.

A Treatment Emergent Adverse Event (TEAE) is defined as an event that has an onset date on or after the first day of exposure to randomised treatment, and no later than seven days after the last day of exposure to randomised treatment.

TEAEs are summarised descriptively, whereas AEs not defined as treatment emergent are presented in listings, including AEs reported in the 30-day follow-up period. The summaries of TEAEs are made displaying the number of subjects with at least one event, the percentage of subjects with at least one event, the number of events and the event rate per 100 subject years of exposure. These summaries are done by seriousness, severity, relation to insulin treatment, relation to technical complaint, premature treatment discontinuation due to AEs, AEs leading to withdrawal from trial and outcome.

Furthermore, summary tables based on system organ class and preferred terms are made for:

- All TEAEs
- Serious TEAEs
- Possibly and probably related TEAEs
- Severe TEAEs
- TEAEs with preferred term that are experienced by at least 5% of the subjects in any treatment arm or by at least 5% of all subjects

For AEs where additional information is recorded, this will be listed.

AEs occurring during the run-in period are considered non-treatment emergent and will be summarised separately.

Number of treatment emergent injection site reactions

Treatment emergent injection site reactions occurring during the trial will be summarised and listed.

Classification of Hypoglycaemia

Treatment emergent: hypoglycaemic episodes will be defined as treatment emergent if the onset of the episode occurs on or after the first day of exposure to randomised treatment, and no later than one day after the last day of exposure to randomised treatment.

Nocturnal hypoglycaemic episodes: episodes occurring between 00:01 and 05:59 both inclusive.

Hypoglycaemic episodes are classified according to the Novo Nordisk classification of hypoglycaemia (see [Figure 4-1](#)) and the ADA classification of hypoglycaemia (see [Figure 4-2](#)).

[figure not shown]
Novo Nordisk classification of hypoglycaemia

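### The hypoglycaemia rate models leave out the run-in episode count (some lost precision, no bias); as a minor point, the calendar-day rule can count V10 meal-test episodes on run-in NovoRapid as treatment emergent

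*Protocol*

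**What the plan says.** **Model.** Protocol 17.4.1.2 and SAP 4.4.1.2 fit a negative binomial regression with log link to severe or BG confirmed episodes: all, daytime, nocturnal and several after-meal windows. The log of treatment-emergent time is the offset. On covariates both say: "The model will include treatment and stratification (T1DM/T2DM), as factors".

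**Data available.** Protocol 8.4.2 says that low or symptomatic glucose values "should be reported in the diary by the subject from V2 to V27 (FU1". V2 opens the 8-week run-in, during which every subject takes NovoRapid and degludec (5.3). The episode record includes "Start date and time of the hypoglycaemic episode" and the date, time and dose of the last bolus.

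**Treatment emergence.** The Protocol counts an episode "if the onset of the episode occurs on or after the first day of exposure to randomised treatment"; the SAP has the same rule, "on or after the first day of exposure to randomised treatment, and no later than one day after the last day of exposure". Both work by day.

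**V10 sequence (Protocol 8.3.1).** On insulin: "For the meal test at V10 the subject must receive the bolus insulin (NovoRapid®) that was used in the run-in period". On order: "Randomisation should not take place before the meal test has ended". An episode during the test must be reported. Once the test is over, the subject is told to stop NovoRapid and start randomised product. One ground for rescheduling the test is: "Any hypoglycaemic episode occurs from midnight before the meal test".

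**The concern.** Comparing safety is the trial's only secondary objective, and the hypoglycaemia rate ratio is its main modelled result. The other modelled endpoints (HbA1c, FPG, meal-test PPG, SMPG measures, responder endpoints, lipids, body weight) all carry a baseline covariate. Hypoglycaemia does not, although its baseline is already collected. If subjects prone to episodes in run-in stay prone afterwards, the run-in count explains part of the between-subject variation and its omission widens the confidence interval.

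The V10 rule is a separate and smaller matter. A severe or <3.1 mmol/L episode after the meal-test NovoRapid dose would be attributed to a product not yet assigned. It has the same expected frequency in both arms, so it pulls the rate ratio towards 1. Such an episode follows a meal, and Protocol 3.1.3 reports that earlier trials found higher faster aspart rates soon after meals.

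**Working it through.** **Plan's own figure.** There is none for hypoglycaemia. The only power statement (81.7% for HbA1c, 135 per arm, SD 1.2, distance to margin 0.42) reproduces with the noncentral t, but has no bearing here.

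**Part 1: precision**

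From the documents: 300 subjects, 1:1, 20% T1DM, 8-week run-in, 16-week treatment.

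Assumed: T1DM rate 3 times the T2DM rate; true rate ratio 1.2; gamma frailty (variance 1) or lognormal frailty (log-SD 1), correlated between periods. The planned model was fitted to simulated data with and without log(run-in count + 0.5).

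| Episodes per subject (16 weeks) | Correlation | Cut in model SE | Equivalent extra subjects, 1/(1 − cut)² − 1 |
|---|---|---|---|
| 3 | 0.3 | 1.4% | 1/0.986² − 1 = 2.9% |
| 3 | 0.5 | 3.7–4.2% (two runs) | 7.8–9.0% |
| 3 | 0.7 | 8.8% | 1/0.912² − 1 = 20% |
| 0.5 | 0.3 | 0.3% | 0.6% |
| 0.5 | 0.5 | 0.8% | 1.6% |
| 0.5 | 0.7 | 1.6% | 3.3% |

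With gamma frailty at 3 episodes, the SE goes from 0.134 to 0.132, 0.128 and 0.122. At that overall rate, nocturnal episodes (assumed 15% of the total) gain 0.7–5.1%.

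A second set of simulations varied the rate (0.5–5), the dispersion (frailty variance 1–2.5) and allowed 10% early discontinuation. It gave cuts of 0.2–9% at correlations 0.3–0.6. Mean estimated ratios were 1.19–1.21 unadjusted and 1.18–1.22 adjusted, against a true 1.20. No bias is visible, as expected for a log-link rate ratio under randomisation if discontinuation is not informative.

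**Part 2: V10 dilution**

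Three main meals a day for 16 weeks is 3 × 112 = 336 meals, against one meal test. If the test carries *m* times the risk of an ordinary meal, then e = m/336 and the observed ratio is (RR + e)/(1 + e). For a true 1.50:

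- m = 1: (1.5 + 0.003)/(1 + 0.003) ≈ 1.499
- m = 10: 1.486
- m = 30: 1.459

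The same can be put in counts, with 150 subjects per arm, B control episodes and a share *q* of subjects with an in-test episode that falls in the analysed category: (1.5B + 150q)/(B + 150q).

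- All episodes, B = 450, q = 1%: 676.5/451.5 = 1.498
- Sparse after-meal window, B = 30, q = 1%: 46.5/31.5 = 1.476
- Sparse after-meal window, B = 60, q = 1%: 91.5/61.5 = 1.488

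The last two imply a large *m*. With B = 30 the ordinary risk is 30/150/336 = 0.060% per meal, so q = 1% means m = 16.8. With B = 60 it is 0.119%, so m = 8.4.

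**The case against.** **The omission is a preference, not an error.** The model is prespecified, the same in both documents, adjusts for the stratification factor and uses an exposure offset. No margin, test or power target rests on hypoglycaemia. All of this stands, and it is why the point is a low-severity improvement.

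**The run-in count may predict poorly.** Basal insulin is optimised in run-in and bolus insulin after V10 (Protocol 5.3, Appendices A1 and A2), and low values in run-in lead to dose reduction. This argues against the high correlations, so a reader should not take the 20% equivalent at 0.7 as the expected gain. At low event rates the gain is close to nil.

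**Model SE is an imperfect yardstick.** Under lognormal frailty, 95% interval coverage ranged over 88–96% for the planned model and 89–96% with the covariate. The empirical SD also fell, by 0–20% at correlations 0.3–0.6, so the direction holds while the exact size is uncertain.

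**V10 exposure is narrow.** An episode between midnight and the test leads to rescheduling. The test starts only at SMPG 4.0–8.8 mmol/L, values of 3.9 or below during it are treated on site, and only severe or <3.1 mmol/L episodes are modelled. A reader might infer that the rule could hide an early after-meal signal. That is not supported: a reading of 1.40 for a true 1.50 needs 5% of subjects to have an in-test episode, all in one window with 30 control episodes (52.5/37.5), which makes the test 84 times as risky as an ordinary meal.

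**Conclusion.** The main point holds as a nearly free gain in precision. Omitting the run-in count leaves the rate ratio unbiased. Including it would cut the model SE by about 1.4–9% at 3 episodes per subject and about 0.3–1.6% at 0.5, for correlations of 0.3–0.7. Every rate, dispersion and correlation is an assumption, because the documents give none. A reader might infer that the planned safety comparison is biased or invalid; nothing in the documents supports that.

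The V10 point holds as a minor gap in definition. It applies only if the first randomised dose is taken on the meal-test date, which the instruction at the end of the test implies but does not guarantee. Its effect is negligible at ordinary-meal risk and reaches 1.476–1.488 in a sparse window only at about 8–17 times that risk. The after-meal windows are affected only if the test meal is recorded as the last main meal. The HbA1c conclusion is unaffected by either point.

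**What to change.** Two additions to SAP 4.4.1.2 before database lock, recorded in SAP 4.5 as changes from the protocol:

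1. **Covariate.** Add log(run-in count of severe or BG confirmed episodes + 0.5) to the all-episodes, daytime and nocturnal models, and keep the planned model as a sensitivity analysis for these three. Leave the after-meal window and severe-episode models as planned: events there are sparse and the gain would be small. The covariate set is then fixed in advance and does not depend on convergence.
2. **V10 rule.** State that an episode on the V10 meal-test date is not treatment emergent if its recorded last bolus is the meal-test NovoRapid dose. The episode form holds the time of the last bolus and the meal-test record holds the clock time of that dose. This works better than a cut at the end of the 180-minute test, because an episode 3–4 hours after the test meal, still on run-in NovoRapid, would otherwise stay in the 0–4 h and >2–4 h windows. It also avoids needing the clock time of the first randomised bolus, for which Protocol 8.1.3 requires only the date. Episodes removed this way belong in the run-in count. The offset can stay: half a day in 113 is about 0.4%, and applies alike to both arms.

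The cost is a few sentences, some programming and one extra model for each of three endpoints, with no new data. Two limits remain. The gain may be very small. Where the last-bolus entry is missing, as it may be on late-completed forms, the SAP should say that the day rule applies.

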**Novo Nordisk**

resulted in a greater early glucose-lowering effect than NovoRapid®, but no statistically significant difference was found between faster aspart and NovoRapid® in total glucose-lowering effect.

In the global phase 3a programme, treatment with mealtime faster aspart effectively improved HbA1c in both subjects with T1DM and subjects with T2DM confirming non-inferiority between faster aspart and NovoRapid®. In a therapeutic confirmatory basal-bolus trial in adult subjects with T1DM, mealtime faster aspart in combination with insulin detemir effectively improved glycaemic control and the reduction in HbA1c was statistically significantly greater than with NovoRapid®. Mealtime faster aspart provided superior PPG control compared to NovoRapid® based on 2-hour PPG increment during a meal test. A statistically significant difference was also demonstrated for 1-hour PPG increment (meal test) in favour of mealtime faster aspart. No statistically significant difference was seen in overall rate of severe or blood glucose (BG) confirmed hypoglycaemic episodes between mealtime faster aspart and NovoRapid®. The rate during the first one hour after start of a meal, constituting a smaller fraction of all severe or BG confirmed hypoglycaemic episodes was statistically significantly higher for faster aspart compared to NovoRapid®. The overall safety profile for faster aspart and NovoRapid® was similar and as expected for insulin aspart.

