In a therapeutic confirmatory basal-bolus trial in adult subjects with T2DM, adding and titrating mealtime faster aspart in combination with insulin glargine also effectively improved glycaemic control. Non-inferiority to NovoRapid® regarding HbA1c change from baseline was confirmed. A statistically significant benefit in 2-hour PPG increment (meal test) could not be confirmed for faster aspart compared to NovoRapid®. A statistically significant difference was demonstrated for 1-hour PPG increment (meal test) in favour of faster aspart compared to NovoRapid®. No statistically significant difference was seen in overall rate of severe or BG confirmed hypoglycaemic episodes between faster aspart and NovoRapid®. The rate during the first two hours after start of a meal, constituting a small fraction of all severe or BG confirmed hypoglycaemic episodes was statistically significantly higher for faster aspart compared to NovoRapid®. The overall safety profile for faster aspart and NovoRapid® was similar and as expected for insulin aspart.

Across the global phase 3a trials, faster aspart was well tolerated with similar safety profile as compared to NovoRapid®, with the most common adverse event being hypoglycaemia, similar to the levels observed with NovoRapid®. The insulin aspart molecule has a well-known safety profile based on more than 19 years of clinical experience. Compared to NovoRapid® faster aspart contains excipients which results in a faster initial absorption of insulin aspart following subcutaneous injection. The added excipients are included in the U.S. Food and Drug Administration's (FDA) list for approved drug products for injections, and no toxicological concerns have been predicted from subcutaneous use in humans at the proposed concentrations. For further details, please refer to the current edition of the Investigator's Brochure (IB) and any updates hereof.

Protocol  
Trial ID: NN1218-4357  
UTN: U1111-1197-8289

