#### 4.1.2 Secondary objective

To compare the safety of faster aspart to NovoRapid® both in combination with insulin degludec with or without metformin in Chinese adults with T1DM or T2DM inadequately treated with a basal-bolus or a premix regimen.

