### General considerations

In general, for endpoints evaluated as a change from baseline and/or where a baseline adjustment is made, baseline is defined as information collected at randomisation (V10). In case a measurement is not available at randomisation, the most recent measurement prior to randomisation will be used as baseline.

All efficacy endpoints will be summarised and analysed using the full analysis set (FAS), unless otherwise stated. Safety endpoints will be summarised using the safety analysis set and analysed using the FAS. The FAS is defined in Section [17.2](#).

Presentation of results from a statistical analysis will include the estimated mean treatment effects (LSMeans) for change from baseline, if applicable. Estimated mean treatment differences (or ratios) will be presented together with two-sided 95% confidence interval (CI) for all endpoints analysed statistically.

The primary objective of the trial is to confirm the effect in terms of glycaemic control of treatment with faster aspart compared to NovoRapid® both in combination with insulin degludec with or without metformin in Chinese adults with T1DM or T2DM inadequately treated with a basal-bolus or a premix regimen, using a non-inferiority approach.

More specifically the upper limit of the 95% confidence interval for the difference between faster aspart and NovoRapid® should be compared to a non-inferiority margin of 0.4%. If it is below or equal to 0.4%, non-inferiority will be considered established and effect demonstrated.

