## Additional analysis

Differences between the two populations will be investigated further by estimating the treatment differences separately for subjects with T1DM and T2DM. These treatment differences will be estimated based on the same data and a similar statistical model as the primary analysis but including interaction terms between treatment, stratification (T1DM and T2DM), and visit.

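### Hypoglycaemia gets one rate ratio across T1DM and T2DM and no summary by type, so an excess confined to T1DM would be strongly diluted

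*Protocol*

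**What the plan says.** The secondary objective (Protocol 4.1.2) begins "To compare the safety of faster aspart to NovoRapid® both in combination with insulin degludec" and covers Chinese adults with either type of diabetes. The count of severe or BG confirmed episodes "will be analysed based on the FAS using a negative binomial regression model with a log-link function", with log exposure time as offset. This is done for eight categories: all, daytime, nocturnal, four windows from the start of the meal (0.5, 1, 2 and 4 hours), and the window from 2 to 4 hours. On the model terms: "The model will include treatment and stratification (T1DM/T2DM), as factors". The SAP repeats this in 4.4.1.2, and its section 4.5 declares no change to the protocol. Neither document mentions an interaction, the dispersion structure or a robust variance.

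On tables: "Separate summaries are made by severity considering all episodes, nocturnal and daytime episodes using Novo Nordisk and ADA classified episodes". Episodes are also summarised by time since the meal. Diabetes type is not among the splits.

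For HbA1c the plan goes further (Protocol 17.3, Additional analysis; SAP 4.3.3): "Differences between the two populations will be investigated further by estimating the treatment differences separately for subjects with T1DM and T2DM". On reporting in general: "Estimated mean treatment differences (or ratios) will be presented together with two-sided 95% confidence interval (CI) for all endpoints analysed statistically".

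**The concern.** A main effect for type allows T1DM and T2DM to have different episode rates, but it forces faster aspart to have the same relative effect in both. If the effects differ, the fitted ratio is a weighted average that describes neither type. At the planned minimum T1DM share, most of the weight falls on T2DM. With no table by type, a reader of the report could not see a T1DM excess in the raw counts either.

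The sponsor's own background (Protocol 3.1.3) gives reason to look. In the T1DM trial, "The rate during the first one hour after start of a meal, constituting a smaller fraction of all severe or BG confirmed hypoglycaemic episodes" was significantly higher with faster aspart. In the T2DM trial the corresponding finding was for a longer window: "The rate during the first two hours after start of a meal, constituting a small fraction of all severe or BG confirmed hypoglycaemic episodes". The results are to support registration in both types, and randomisation is stratified by type, so comparisons within type are randomised comparisons.

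**Working it through.** **The plan's own figure.** No power or precision is given for hypoglycaemia. The only power figure is for HbA1c, and it reproduces. With 135 per arm, SD 1.2, margin 0.4 and difference −0.02, the noncentrality is 0.42 / (1.2 × √(2/135)) = 0.42 / 0.146 = 2.88, giving 81.7%. Then 270 / 0.9 = 300.

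**Inputs from the documents.** 300 randomised 1:1 (Protocol 11 and 17.1); at least 20% T1DM (6.1), so 60 T1DM and 240 T2DM at the floor; 16 weeks = 16/52 year.

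**Assumptions, not in the documents.** Episodes per patient-year in T1DM/T2DM: 40/10, 20/5, 10/10 and 6/1.5. Negative binomial dispersion k of 1 or 2, and unequal values where stated.

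**1. Dilution.** The pooled log rate ratio is approximately w·log(RR in T1DM) + (1 − w)·log(RR in T2DM). Each type is weighted in proportion to n / (1/μ + k), where μ is the mean count. For rates 40/10 and k = 1:
- μ = 40 × 16/52 = 12.31 in T1DM and 3.08 in T2DM.
- Information: 60 / (0.081 + 1) = 55.5 and 240 / (0.325 + 1) = 181.1.
- w = 55.5 / 236.6 = 0.23.
- T1DM ratio 1.5, T2DM ratio 1.0: exp(0.235 × 0.405) = 1.10.

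All four rate settings at 20% T1DM and k = 1:

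| Rates T1DM/T2DM | w | 1.5 / 1.0 | 2.0 / 1.0 | 1.0 / 1.5 |
|---|---|---|---|---|
| 40/10 | 0.23 | 1.10 | 1.18 | 1.36 |
| 20/5 | 0.26 | 1.11 | 1.20 | 1.35 |
| 10/10 | 0.20 | 1.08 | 1.15 | 1.38 |
| 6/1.5 | 0.34 | 1.15 | 1.27 | 1.31 |

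The last three columns are pooled ratios for the true T1DM / T2DM ratios shown. Taking k = 2 stays within these ranges. A T1DM ratio of 1.5 with 0.9 in T2DM pools to 1.00–1.07. An excess confined to T2DM is diluted much less. At 40% T1DM, a 1.5 / 1.0 pattern pools to 1.18–1.26.

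**2. How often the pooled interval would show it.** The planned model, with one dispersion, was fitted to simulated trials of 300 subjects (20% T1DM). With a T1DM-only ratio of 1.5, the 95% interval lay above 1 in 11.9% of trials (rates 40/10, k 1/1), 8.7% (40/10, k 0.7/2) and 10.9% (20/5, k 0.7/2). A separate run with mean counts of 8–12 in T1DM and 1–2 in T2DM gave 13–14%. With a T1DM-only ratio of 2.0 the figures were 17–26%. At 40% T1DM (20/5, k 1/1, ratio 1.5) the figure rose to 31%.

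**3. Coverage with one common dispersion.** Simulated at 60/240 subjects and rates 40/10, with no treatment effect:

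| k T1DM/T2DM | Model-based coverage | Robust variance |
|---|---|---|
| 1/1 | 94.5% | 94.4% |
| 0.7/2 | 94.1% | 94.5% |
| 0.5/3 | 92.8% | 94.4% |
| 2/0.7 | 94.5% | 94.2% |
| 3/0.5 | 94.1% | 94.4% |

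At the lower mean counts of 8–12 and 1–2, coverage was 94.8% for k 0.6/1, 94.3% for 0.8/2 and 91.4% for 0.6/3.

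**4. What estimates by type would give.** Var(log RR) = 4(1/μ + k)/n. For T1DM at rates 40/10 and k = 1, the SE is √(4 × 1.081 / 60) = 0.27, so the 95% factor is exp(1.96 × 0.27) ≈ 1.7. Across the four rate settings with k of 1 to 2, the factor is 1.7–2.2; at somewhat lower assumed dispersion it is about 1.6. Power to detect an interaction is 13–26% for a ratio of rate ratios of 1.5 and 29–62% for 2.0. For a T1DM ratio of 1.5, the chance that the T1DM interval lies above 1 is Φ(0.405/0.2685 − 1.96) = 33% at k = 1, and Φ(0.405/0.3725 − 1.96) = 19% at k = 2 (both at rates 40/10).

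**The case against.** The case for leaving the plan alone has weight. Hypoglycaemia is a supportive secondary safety endpoint with no hypothesis or margin, so no confirmatory decision rests on this ratio. Calling it the main safety comparison would go beyond the documents. The objective is pooled, type is already in the model, and the windows in which the earlier trials saw an excess are all analysed.

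A reader might also infer from Protocol 3.1.3 that the effect is known to differ by type. It does not show that. Both trials point the same way, they used different basal insulins, neither found a significant difference in the overall rate, and significance in different windows of separate trials is not evidence of effect modification. Finally, eight categories by two types make 16 ratios, those for T1DM imprecise, which invites chance findings.

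All of this stands as a limit on how results by type should be read. It does not justify leaving them out. Descriptive tables need no power, ratios labelled as estimates make no claim of a test, and the plan already accepts this kind of estimate for HbA1c.

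**Conclusion.** The point holds: the plan gives one rate ratio per hypoglycaemia category and no view of the data by type. At the 20% T1DM floor, a T1DM-only ratio of 1.5 would appear as about 1.1 (1.08–1.15), and the pooled interval would show it in about 9–14% of trials. These figures rest on assumed rates and dispersions, and the dilution weakens if more T1DM subjects are recruited.

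A reader might infer that the pooled interval is too narrow whenever dispersion differs. That is not supported. The documents do not state the dispersion structure; one common parameter is only the usual default. Under that default, coverage is close to nominal for small differences and falls to about 91–94% when dispersion differs several-fold, depending on which type is more dispersed and on the rates. This is a secondary reason to specify the variance, not the substance of the point.

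**What to change.** In Protocol 17.4.1.2 and SAP 4.4.1.2:

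- Tabulate subjects with an episode (N, %), episodes (E) and rate (R) by diabetes type and arm for the planned categories.
- Add a treatment-by-type interaction to the negative binomial models, or fit them by type, where episode counts allow. Report the rate ratio with 95% CI for each type as an estimate, not a powered test.
- Keep the pooled ratio, and specify a type-specific dispersion or a robust variance for it.

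The cost is SAP wording and extra tables, with no new data, visits or alpha. The downside is imprecision: with about 30 T1DM subjects per arm, intervals are about ×/÷ 1.6–2.2, and the shortest meal windows may support tables only.
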